### 11.1.6 Blood Sampling for Determination of Factor IX Level

At each blood sampling time point whole blood will be collected in S-Monovette® tubes (Sarstedt, Nümbrecht, Germany) containing 3.2% trisodium citrate, or equivalent blood drawing equipment (eg, Vacutainer tubes), and immediately mixed. **The citrated whole blood samples will be capped and transported at room temperature (ie, 20-25°C) to the local clinical laboratory for centrifugation, processing, and storage.** Monovettes must be kept in an upright position at all times to avoid leakage.

For all clotting assays, citrated whole blood will be spun in a **refrigerated centrifuge (2 to 8°C)** at  $\geq 2000 \times g$  gravity for approximately 20 minutes in capped tubes **within 2 hours of collection**. The plasma supernatant will be re-centrifuged at the same rate and duration to ensure removal of platelets and other particulate matter.

At least three aliquots of 0.6 mL of the centrifuged, citrated plasma will be pipetted into appropriate storage tubes, capped, labeled, and **stored in a freezer at  $\leq -70^{\circ}\text{C}$ , ideally within 15 minutes, but no later than 30 minutes after processing.**

All citrated plasma samples will be stored and shipped to the central laboratory at  $\leq -70^{\circ}\text{C}$  for testing. All samples will be maintained capped to the greatest extent possible. All citrated plasma samples will be assayed for FIX activity using the one-stage aPTT-based assay method.

## 11.2 TGA Testing

Blood samples for TGA testing will be taken at the same time points as for FIX activity determination in a subset of subjects. Subjects will be infused with  $75 \pm 5$  IU/kg of BAX326 during the regular study visits. Upon completion of the infusion, the butterfly catheter should be flushed with at least 2 mL of saline solution. The same criteria as described in Section 11.1 for determination of FIX activity also apply for TGA testing. TGA testing will only be performed in subjects 12 years and older.

### 11.2.1 Determination of TGA Parameters During PK

Blood samples for TGA parameters will be collected at the same time points as described in Section 11.1.1 for the PK assessment of FIX and are provided below in **Table 11.2-1**.

---

**Table 11.2-1**  
**Time Points for Determination of TGA Parameters During PK for FIX**

Pre-infusion	0-30 minutes prior to infusion
Infusion of $75 \pm 5$ IU/kg BAX326	
Post-infusion	$30 \pm 5$ minutes
	$9 \pm 3$ hours
	$24 \pm 6$ hours
	$48 \pm 6$ hours
	72 (- 6) hours

---

Note: The assessment of TGA parameters must be performed at least 5 days (120 hours), preferably 7 days following the previous dose of a FIX product and the subject must not actively bleed.

Samples for measurement of TGA testing taken through 6 hours post-infusion will be obtained from an extremity different from that used for the infusion of IP, using a 21- or 23-gauge thin-walled needle. Where needed, the phlebotomy site will be kept patent via an infusion of normal saline. In this event, at least 2 mL of blood will be collected and discarded before collection of the next test sample into a fresh syringe.

If the subject has a central venous catheter, the central line should be used to administer the infusion and a peripheral venipuncture should be used to collect the blood samples. In the event that a blood sample must be drawn through the central line used for administration of IP, the line must first be flushed with 5 mL normal saline or other suitable catheter flush solution that does not contain anticoagulant. At least 5 mL of whole blood must be collected and discarded prior to obtaining the sample.

### **11.2.2 Pre- and Post-Infusion TGA Parameters Over Time in Subjects Receiving PK-Tailored Prophylaxis**

TGA parameters will be determined pre- and post-infusion of BAX326 at the following visits in all or approximately 20 subjects  $\geq$  12 years and receiving PK-tailored prophylaxis:

- At ED 1 – for transitioning subjects who have undergone a PK study in BAX326 Pivotal, BAX326 Pediatric or BAX 326 Surgery
- At Week 4  $\pm$  1
- At Month 3  $\pm$  1 week
- At Month 6  $\pm$  1 week

---

**Table 11.2-2**  
**Time Points for Determination of Pre- and Post-Infusion TGA Parameters Over Time**

Pre-infusion	0-30 minutes prior to infusion
Infusion of BAX326, at dose of $75 \pm 5$ IU/kg	
Post-infusion	30 minutes $\pm$ 5 minutes

---

Samples for measurement of TGA parameters will be obtained from an extremity different from that used for the infusion of IP.

### **11.2.3 Additional Determination of TGA Parameters in Subjects Receiving Modified Prophylaxis**

In addition, TGA parameters will also be determined within this 6-month period pre- and post-infusion at 4 different timepoints depending on the frequency of weekly prophylactic infusions **without the requirement of a wash-out period**. The pre- and post-infusion blood draws should occur such that they reflect the dosing interval. The TGA determination should coincide with the additional FIX activity level measurements as described in Section 11.1.5.

#### 11.2.4 TGA Testing in Subjects Receiving Standard (Twice Weekly) Prophylaxis

In approximately 20 subjects, TGA parameters concurrent with the determination of pre- and post-infusion levels of FIX activity will be determined at 4 different time points during a 6-month period with regular, twice weekly prophylactic infusions, **without the requirement of a wash-out period**:

On 2 occasions, these should be assessed **3 days** after a prophylactic infusion of BAX326, ie, before and after the subsequent prophylactic infusion of BAX326, and on the other 2 occasions **4 days** after a prophylactic infusion of BAX326, ie, before and after the subsequent prophylactic infusion of BAX326, as shown in [Table 11.2-3](#):

---

**Table 11.2-3**  
**Time Points for Determination of Pre- and Post-Infusion TGA Parameters**  
**During Regular, Twice-Weekly Prophylaxis**

---

Example: **3 days** after last prophylactic infusion:

Last prophylactic infusion  
approx 72 hours ago  
(eg: Monday morning)

→ Subsequent prophylactic infusion approx 72 hours later  
(eg: Thursday morning):

Pre-infusion	0-30 minutes prior to infusion
Infusion of regular prophylactic infusion	
Post-infusion	30 ± 5 minutes

Example: **4 days** after last prophylactic infusion:

Last prophylactic infusion  
approx 96 hours ago  
(eg: Thursday morning)

→ Subsequent prophylactic infusion approx 96 hours later  
(eg: Monday morning):

Pre-infusion	0-30 minutes prior to infusion
Infusion of regular prophylactic infusion	
Post-infusion	30 ± 5 minutes

In addition, pre- and post-infusion TGA parameters will also be determined concurrent with FIX activity determination at the regular study visits during the 6- month period following a wash-out period and following administration of  $75\pm5$  IU/kg of BAX326 (ie, in total 3 times: at Month  $3 \pm 1$  week, at Month  $6 \pm 1$  week and at Month  $9 \pm 1$  week).

### **11.2.5 Blood Sampling for TGA Testing**

At each blood sampling time point, 3 mL of whole blood will be collected to obtain 2 aliquots of at least 0.6 mL. A detailed description of the blood sampling procedure and processing will be provided in the Laboratory Manual.

## **11.3 Hemostatic Efficacy**

In all cases, the treatment with BAX326 will be at the discretion of the investigator and will consist of one of the following treatment options:

- standard prophylactic treatment with twice weekly administrations of 50 IU/kg (range 40-60 IU/kg which may be increased to 75 IU/kg [ $\geq 12$  years of age] or 40-80 IU/kg [ $< 12$  years of age]),
- modified prophylaxis,
- PK-tailored prophylactic treatment based on subject's individual PK, or
- on-demand treatment only (not applicable for newly recruited subjects).

The regimen for prophylactic and on-demand treatment should be based on the guidance as provided in Section [8.6.3 'Description of Treatment'](#). The following information will be recorded by the subject, the subject's legal representative (for home treatment) or by authorized, qualified personnel at the participating site (for hospital-based treatment in case of a bleeding episode):

- Location of bleed, ie, joint, soft tissue, muscle, body cavity, intracranial, other
- Type of bleed, ie, spontaneous, injury, unknown
- Severity of bleed, ie, minor, moderate, major, life/limb threatening
- Date and time of onset of bleed
- Date and time of each infusion of BAX326 required to achieve adequate hemostasis
- Date and time of resolution of bleeding episode

**Note:**

**It is critical to inform the subject that 'resolution of bleed' means 'cessation of bleed' and not 'cessation of all bleed-related symptoms'.**

- Type and number of analgesics required
- Overall clinical efficacy rating according to the rating scale as described in [Table 11.3-1](#) at resolution of bleed.

Table 11.3-1 Rating Scale for Treatment of Bleeding Episodes	
Excellent	Full relief of pain and cessation of objective signs of bleeding (eg, swelling, tenderness, and decreased range of motion in the case of musculoskeletal hemorrhage) after a single infusion. No additional infusion is required for the control of bleeding. Administration of further infusions to maintain hemostasis would not affect this scoring.
Good	Definite pain relief and/or improvement in signs of bleeding after a single infusion. Possibly requires more than 1 infusion for complete resolution.
Fair	Probable and/or slight relief of pain and slight improvement in signs of bleeding after a single infusion. Required more than 1 infusion for complete resolution.
None	No improvement or condition worsens.

If a bleed occurs following resolution of the bleed, it will be considered to be a 'new' bleed and recorded accordingly.

Subjects will resume their prophylactic treatment regimen the next scheduled day after the last therapeutic infusion for the treatment of a bleeding episode.

Details pertaining to all home treatments for each bleed, including response to treatment, will be recorded by study subjects or the subject's legal representative in subject diaries provided by the study sponsor. At each study visit the investigator will review together with the subject the response to treatment and evaluate the hemostatic efficacy rating. Any inconsistency between the efficacy rating and the number of infusions required to treat a bleeding episode, or a response to treatment rated as "none" must be immediately clarified. If two or more responses to treatment are rated with "fair", the investigator may re-evaluate the dosing regimen, and the time from bleeding onset to start of treatment. In case more than one infusion was given to treat a bleeding episode, but the treatment was rated with "excellent", information should be provided about the severity of the bleeding episode and/or whether additional infusions were given to maintain hemostasis. If infusions were given to maintain hemostasis after resolution of bleed, this should be recorded accordingly in the eCRF. **It is important to clearly indicate after which infusion the bleed stopped.** This may not necessarily coincide with the cessation of objective signs of bleeding, such as pain or swelling, since the absorption of blood would still be ongoing. Particularly in the case of severe hemophilic arthropathy and/or previous

joint surgery combined with severe bleeds, it is more difficult to define exactly the time point of the cessation of the bleed. If pain persists despite several infusions of BAX326, the presence of a bleed should be verified. It may become necessary to re-discuss the rating with the subject to ensure that the Rating Scale is fully understood. Cases of bleeding episodes requiring only one infusion but with a response to treatment rated with “fair” should also be evaluated.

If, at any time during the course of the study, a subject’s bleeding episode does not adequately respond to BAX326 therapy, he/she will be evaluated for the presence of inhibitory or total binding antibodies to FIX and clinically managed at the discretion of the investigator (see Section 12.7.1). In addition, AEs and the details of concomitant medication use coincident with the treatment of all acute bleeds will be recorded. Note that bleeding episodes are not to be reported as AEs (Section 12.3). Any non-study FIX therapy or hemostatic product use administered for a bleeding event will be recorded on the appropriate section of the subject’s diary and the eCRF. The use of a FIX concentrate other than BAX326 will disqualify the subject from further participation in the study.

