7.2 Analysis of Secondary Efficacy Outcome Measure

7.2.1 Treatment of Bleeding Episodes

Summary statistics will be provided for the overall hemostatic efficacy rating at resolution of bleed as well as for the number of infusions per bleeding episode. These tables will be also presented by bleeding site (joint/non-joint), cause (spontaneous/injury) and severity (minor, moderate, major, and life/limb-threatening). These subgroup analyses will be performed on the FAS only.

As a sensitivity analysis to the assumption of independency between bleeds within the same subject, these summary tables will be also created with the assessment of the first bleed within a specific treatment regimen for each subject. This sensitivity analysis will be performed on the FAS only (and not by bleeding site, cause and severity).

Bleeding episodes, for which any hemostatic product other than BAX326 had to be used, will not be considered.

These tables will be created by treatment regimen as well as for all treatment regimens together.

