7.2.2 Prophylaxis: Annualized Bleed Rate

The ABR will be calculated as follows:

$$\frac{\text{Number of bleeding episodes}}{\text{Observed treatment period in days}} * 365.25.$$

The ABR will be listed and summarized only for subjects who have adequate treatment time for bleeding rate assessment. For subjects on prophylaxis, a subject is considered to have an adequate treatment time for bleeding rate assessment if the observation period with BAX326 in this study within the respective treatment regimen was a minimum of 3 months (treatment period for surgery and bleeding period are not counted).

The observation period for prophylactic treatment is considered as the time between the first and the last prophylactic infusions. For transitioning subjects, infusions prior to eligibility assessment will count in case the treatment regimen is the same as the regimen the subject receives after eligibility is confirmed. The treatment period for surgery as well as the bleeding period will be excluded from the calculation of observation period in the calculation.

Additionally, the ABR will also be calculated for subjects with on-demand treatment. The observation period for on-demand treatment is considered as the time between the date of eligibility (or the date of switching to on-demand for subjects who were on prophylaxis before) and the end of observation period.

These tables will be created by treatment regimen.

ABR will be also presented by bleeding site (joint/non-joint), cause (spontaneous/injury), severity (minor, moderate, major, and life/limb-threatening), presence of target joints and FIX activity levels at screening. These subgroup analyses will be performed on the FAS only.

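### An early re-bleed at the same site counts as a new bleed and no analysis joins the two, so infusions per bleed and the first rating can look too favourable and ABR too high

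*Protocol*

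**What the plan says.** **Counting rule.** Protocol 11.3, below Table 11.3-1: "If a bleed occurs following resolution of the bleed, it will be considered to be a 'new' bleed and recorded accordingly". No minimum interval is given and the bleed need not be at a different site.

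**Resolution.** The note in the same section tells subjects that "resolution of bleed' means 'cessation of bleed' and not 'cessation of all bleed-related symptoms". The overall rating is given at that moment.

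**Rating scale.** Table 11.3-1 judges the response after a single infusion. For the top category it adds "No additional infusion is required for the control of bleeding". No category requires a period free of re-bleeding.

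**Visit review.** Protocol 11.3 requires prompt clarification of "Any inconsistency between the efficacy rating and the number of infusions required to treat a bleeding episode" and of a rating of None. It also looks at repeated Fair ratings, a single-infusion Fair, and an Excellent with more than one infusion. A later re-bleed is not listed as a trigger.

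**Analysis.** SAP 7.2.1: "Summary statistics will be provided for the overall hemostatic efficacy rating at resolution of bleed" and, in the same sentence, "as well as for the number of infusions per bleeding episode". SAP 7.2.2 divides the number of bleeding episodes by observed days and multiplies by 365.25, with surgery and bleeding periods removed from the denominator. Its restriction concerns observation time only: "The ABR will be listed and summarized only for subjects who have adequate treatment time for bleeding rate assessment". Neither section defines an episode or gives a joining rule.

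**Data collected.** Protocol 11.3 lists a location category, date and time of onset, date and time of each infusion, and "Date and time of resolution of bleeding episode". Protocol 10.5 says the diary also records the site of the bleed.

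**The concern.** Suppose a joint stops bleeding after one infusion and bleeds again some hours later. Under the rule this is two episodes. The first is complete, with one infusion and possibly a rating of Excellent or Good, although hemostasis did not hold. The second has its own infusion count and rating.

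Three secondary outcomes are affected, and not in the same direction. Infusions per bleed falls and the rating of the first bleed stands, both of which flatter treatment of bleeds. ABR rises, which makes prophylaxis look worse. Weight-adjusted consumption per bleeding event (SAP 7.2.3) shares the episode denominator.

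The boundary between episodes is also uncertain. Protocol 8.6.3.2 and 11.3 both concede that the moment a bleed stops is hard to fix in severe arthropathy or after joint surgery. In the pivotal study, one of the two sources of Cohort 1, 88% of subjects had arthropathy and 66% had target joints at screening (Protocol 6.4.1).

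**Working it through.** **No plan figure to reproduce.** The documents give no re-bleed rate, and the sample size has no statistical basis. The pivotal figures in Protocol 6.4.1, used below only as an illustrative base, correspond to whole counts out of 249 bleeds: 239/249 = 96.0% Excellent or Good, 153/249 = 61.4% with one infusion.

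**Pooled effect.** Let r be the share of recorded bleeds that are early same-site re-bleeds (assumed). Joining them turns N recorded bleeds into N(1 − r) episodes, with total infusions and follow-up unchanged.

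- Overstatement of the pooled bleed rate: 1/(1 − r) − 1 = r/(1 − r).
- Recorded mean infusions per bleed = (1 − r) × joined mean, an understatement of r.

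| r (assumed) | Pooled rate overstated by | Mean infusions understated by |
|---|---|---|
| 0% | 0% | 0% |
| 5% | 0.05/0.95 = 5.3% | 5% |
| 10% | 0.10/0.90 = 11.1% | 10% |
| 15% | 0.15/0.85 = 17.6% | 15% |

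**Per-subject ABR.** The SAP summarises ABR subject by subject, so the pooled ratio does not carry over. For one subject, splitting one episode into two doubles ABR:

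- over 90 days, 365.25/90 = 4.06 becomes 8.12;
- over 182.6 days, 2.0 becomes 4.0;
- over 90 days with 2 days removed per bleed (assumed), 365.25/88 = 4.15 becomes 2 × 365.25/86 = 8.49.

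A subject with no bleed or one bleed has no pair to join. In the pivotal study 24 of 56 subjects on prophylaxis (42.9%) had no bleed. The median ABR of 1.99 over a median 6 months is about one bleed (1.99 × 0.5 ≈ 1.0). The median could therefore stay still while the mean moves.

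**Ratings.** Let k bleeds out of 249 be re-bleeds. If the worse rating of each pair is kept, and at least one of the two was Excellent or Good, joining removes one favourable rating and one episode: (239 − k)/(249 − k). If instead every joined pair were declared a failure, and both parts had been rated favourably: (239 − 2k)/(249 − k). If both parts had one infusion, the one-infusion share is (153 − 2k)/(249 − k).

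| k (assumed share) | Worse rating kept | Every pair a failure | One infusion |
|---|---|---|---|
| 0 (0%) | 96.0% | 96.0% | 61.4% |
| 12 (5%) | 227/237 = 95.8% | 215/237 = 90.7% | 129/237 = 54.4% |
| 25 (10%) | 214/224 = 95.5% | 189/224 = 84.4% | 103/224 = 46.0% |
| 37 (15%) | 202/212 = 95.3% | 165/212 = 77.8% | 79/212 = 37.3% |

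The combined Excellent-or-Good share hardly moves when the worse rating is kept. The last two columns are extreme cases. The shift from Excellent to Good cannot be computed, because Protocol 6.4.1 gives only the two categories combined.

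**First-bleed analysis.** SAP 7.2.1 repeats the tables with each subject's first bleed in a regimen, to test independence between bleeds. If that first bleed re-bled, the analysis keeps the first part and drops the second.

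**The case against.** The strongest objection is that the effect may be nil. No re-bleed rate is given, and at 0% nothing changes. The outcomes are secondary and descriptive in an uncontrolled study, and the primary outcome, related adverse events, is untouched. This stands, and it limits the point to a sensitivity analysis.

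Safeguards exist. Excellent requires full pain relief and cessation of objective signs, the investigator evaluates ratings at each visit and may re-discuss them, and Protocol 10.5 requires implausible diary entries to be clarified. These help, but none is triggered by a re-bleed, and none joins the episodes.

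A reader might infer three stronger things that the documents do not support:

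- **That ratings are heavily inflated, for example 96.0% against 90.7%.** This requires every joined pair to count as a failure. Table 11.3-1 has no such rule, and Good allows more than one infusion.
- **That the study's ABR is overstated by 5% to 18%.** Those are pooled figures for an assumed share of 5% to 15%, not a finding about mean or median ABR.
- **That the rule favours the product throughout, or that the first-bleed analysis is defective.** The ABR error is conservative, and the first-bleed analysis was written for a different question.

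A joining rule can also do harm. A fresh injury to the same joint should not be merged, a window starting from an infusion given only to maintain hemostasis would reach too far, and joining on the location category in Protocol 11.3 could merge different joints. No interval is given in the documents, so any single cut-off would be arbitrary.

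**Conclusion.** The concern holds as a gap in the analysis plan. As written, an early re-bleed at the same site becomes a separate episode, and neither the visit review nor the SAP brings the two together. Where this happens, infusions per bleed is understated, the first bleed can keep a favourable rating, and ABR is overstated.

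The size is unknown. For an assumed 0% to 15% of recorded bleeds, the pooled bleed rate is overstated by 0% to 18% and mean infusions per bleed understated by 0% to 15%, with total infusions and follow-up held fixed. Per-subject ABR may shift by more or less. The effect on the combined Excellent-or-Good share is probably small: under one percentage point on the pivotal counts when the worse rating is kept. The effect on the Excellent category alone cannot be judged from the documents.

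**What to change.** Leave the primary tables as planned and add one sensitivity analysis to SAP 7.2.1 and 7.2.2:

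- **Same site.** Join bleeds only at the same specific site, such as the same joint, not merely the same location category. First confirm that the recorded site variable allows this. Protocol 10.5 names a site, and the same-target-joint criterion in 8.6.3.1 presupposes joint-level detail, but the level recorded is not stated.
- **Cause.** Do not join when the second bleed is recorded as due to injury.
- **Interval.** Use several stated intervals, for example 24, 48 and 72 h, from resolution or from the last infusion needed to control the bleed. Do not count infusions given only to maintain hemostasis. These are analysis choices and do not come from the documents.
- **Outcomes.** Sum the infusions for control and count one episode for ABR. State how the bleeding period of a joined episode is removed from the denominator. Keep the worse rating, but do not allow a joined episode to be Excellent, because Table 11.3-1 requires that control needed no further infusion.
- **Reporting.** Give the number of joined pairs at each interval.

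The cost is one derived episode variable and a repeat of a few tables, with no new data if the site variable is adequate. If pairs are rare, the count shows that the results are robust.
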